9.2.2. Baseline: PROs

Patients aged 13 or over should complete the PROs including Sarcoma Assessment Measure (SAM), EORTC-QLQ-C30, TESS and GRC within 2 weeks after registration and prior to starting treatment (if possible). The SAM booklet (Sarcoma Assessment Measure (SAM), EORTC-QLQ-C30, TESS and GRC) can be completed over the phone as well as by post or in person.

9.2.3. Baseline: Routes to Diagnosis

The patient routes to diagnosis questionnaire should be given to the patient or parent/legal guardian at baseline only. It must be completed in person and not undertaken over the phone or posted. It takes around 20 minutes to complete and should be returned to site for data entry.

- Patients aged 13 or over should complete the Patient routes to diagnosis questionnaire within three months of registration.
- For patients aged less than 13, the parents or legal guardians should complete the Patient routes to diagnosis questionnaire within three months of registration.

The GP routes to diagnosis questionnaire and information sheet should be sent (by email or post) to the patient's GP at baseline and should be returned to site for data entry. If not returned to the site within four weeks the GP should be sent one reminder.

9.2.4. Baseline: Research Samples

(SEE SECTION 10 FOR SUMMARY)

All patients

- Whole blood sample for germline DNA (preferably collected at study entry, but may be collected at any point during the study)
- Whole blood sample for ctDNA, DNA methylation profiling/future research (optional)
 - NB if patient has started chemotherapy prior to study entry this sample may still be collected
 - If the baseline ctDNA sample is missed for any reason, please continue with the on treatment, end of treatment and follow up samples.
- Surgery site to ship diagnostic FFPE tissue to RNOH (coordinated by UCL CTC)
- Collect information about frozen tumour samples (where sample stored, reason sample not taken if applicable)

Patients receiving neoadjuvant chemotherapy

• Whole blood samples for CTCs, collected prior to the start of chemotherapy

Patients on PBMC substudy (UCLH site only)

Whole blood samples for PBMCs, collected prior to the start of neoadjuvant chemotherapy.

9.3. During Treatment

If patient does not receive treatment for any reason, skip to section 9.5 (Follow up).

The reason why no treatment was given should be documented.

9.3.1. During Treatment: Clinical Data

During treatment, data should be collected at the end of neoadjuvant chemotherapy, at surgery, at the end of adjuvant chemotherapy, after radiotherapy and at the end of treatment.

The following details should be collected at the end of neoadjuvant chemotherapy:

- Details of chemotherapy given, including drug doses, dates and reason(s) for reductions, delays or discontinuation
 - If neoadjuvant chemotherapy not given, reason should be documented
- Disease status (if assessment carried out)
- Adverse reactions: assessed only in relation to study procedures, e.g. venepuncture, biopsy for research, when applicable

The following details should be collected prior to surgery:

- WHO performance status (patients ≥ 16) or Lansky performance status
- Blood Biochemistry: CRP, albumin, ALP, LDH, creatinine

- Haematology: Hb, ANC, lymphocytes, platelets
- Preoperative imaging
 - Date of MRI
 - Date of CT, if performed
 - Date and type of other imaging, if applicable
 - Disease status

The following surgical details should be collected following surgery for ALL patients on the Surgery eCRF:

- Date and time of surgery
- · Hospital where surgery performed
- Type of surgery (amputation, limb sparing etc.)
- Details of surgical procedure (which anatomical structures removed, use of antibiotics, details on blood loss, whether central line in situ, type of reconstruction, surgical margin assessment etc.)
- ASA classification
- Postoperative complications (wound complications, dehiscence, infection or haematoma requiring return to theatre, thromboembolism, deep implant infection etc.)
- If surgery was planned but not done the reason should be documented.

Pathology

- Maximum dimension on pathology report
- Margins: bone margin, narrowest margin in mm
- Lymphovascular invasion
- Response to chemotherapy, % necrosis
- Was a fresh/frozen specimen stored?
 - If so, where?
 - If not, why not?
- Adverse reactions: assessed only in relation to study procedures, e.g. venepuncture, biopsy for research, when applicable

The following details should be collected at the end of adjuvant chemotherapy:

- Details of chemotherapy given, including drug doses, dates and reason(s) for reductions, delays or discontinuation
- If adjuvant chemotherapy not given, reason
- · Was mifamurtide given? If not, reason why
- Disease status (if imaging assessment carried out)
- Adverse reactions: assessed only in relation to study procedures, e.g. venepuncture

The following details should be collected after radiotherapy (if given):

- Details of radiotherapy, including indication (primary, palliative or both), modality, technique, dates, doses and fractionation
- Adverse reactions: assessed only in relation to study procedures

If patients undergo thoracotomy at any time, please provide:

- Date, place of surgery;
- type of resection; side of resection; no of lesions resected;
- was metastatic disease verified histologically?
- no. of verified lesions; resection margins
- Was sample stored for research?
 - if so, where is it stored?

9.3.2. During Treatment: Research Samples

All patients

- Whole blood sample for ctDNA, DNA methylation profiling/future research (optional)
 - For patients receiving MAP chemotherapy collect Pre cycle 2 day 21 methotrexate (ideally up to 3 to 7 days prior/14 days post cycle 2) or pre surgery if this is not possible
 - For patients receiving AP or other chemotherapy, collect pre cycle 3 (ideally up to 3 to 7 days prior and 14 days post cycle 2) **or pre surgery** if this is not possible
 - If the baseline ctDNA sample was missed for any reason, please continue with the On treatment, End of treatment and Follow up samples.

Patients receiving neoadjuvant chemotherapy

- Whole blood sample for CTCs
 - Only to be taken if the baseline CTC sample was collected.
 - For patients receiving MAP chemotherapy collect Pre cycle 2 day 21 methotrexate (ideally up to 3 to 7 days prior/14 days post cycle 2) or pre surgery if this is not possible
 - For patients receiving AP or other chemotherapy, collect pre cycle 3 (ideally up to 3 to 7 days prior and 14 days post cycle 2) or pre surgery if this is not possible

Patients on PBMC substudy (UCLH site only)

• Whole blood samples for PBMCs, collected prior to surgery

9.4. End of Treatment

 For the purpose of clinical data, sample and PROs collection End of Treatment is defined as end of chemotherapy, and not end of treatment with Mifamurtide

9.4.1. End of Treatment: Clinical data

The following details should be collected at the end of treatment:

- Total number of cycles of chemotherapy and doses
- Total number of mifamurtide cycles
- If terminated early, provide reason
- Imaging performed, date, modality, result
- Blood Biochemistry: CRP, albumin, ALP, LDH, creatinine
- Haematology: Hb, ANC, lymphocytes, platelets
- Disease status
- Adverse reactions: assessed only in relation to study procedures, e.g. venepuncture, biopsy for research.

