2.3. Improving systemic therapy and introduction of new treatments

Improvements in systemic therapy for OS are needed urgently. The unmet needs which ICONIC addresses include: addressing variation in delivery of, and response to, standard therapies including chemotherapy and mifamurtide through evaluation of concordance with a national algorithm; identifying factors influencing decision making in specific subgroups such as those aged over 40 or with unresectable primary tumours; stimulating the development of new pilot therapeutic interventions in areas identified by analysis of clinical data on chemotherapy delivery and toxicity, especially for less common subgroups; promotion of access for individual patients to current trials through network impact; provision of the infrastructure shown to be necessary to provide a platform for new agent studies. Examples include: in another rare bone cancer, Ewing sarcoma, the novel multi-arm, multistage (MAMS) study: rEECur (ISRCTN36453794), supported by EU funding to rapidly evaluate treatments at recurrence and compare new agents to standard of care; in lung cancer, driven by the findings from TRACERx, DARWIN 1: Deciphering Afatinib Response and Resistance with INtratumour heterogeneity study (NCT02183883).

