10.5. Whole blood samples for ctDNA, methylation profiles and future research

Whole blood samples for future research including measurement of cell free DNA and analysis of methylation profiles may be collected from all patients who have consented to this. **These samples are optional.**

10.5.1. ctDNA Collection time points

Samples from all patients consenting to this should be collected at the following timepoints (at the same time that routine bloods are taken):

- Baseline (prior to start of neoadjuvant chemotherapy if applicable)
- During treatment:
 - For patients receiving **MAP** chemotherapy collect Pre cycle 2 day 21 methotrexate (ideally up to 3 to 7 days prior and 14 days post cycle 2) or pre surgery if this is not possible
 - For patients receiving **AP or other** chemotherapy, collect pre cycle 3 (ideally up to 3 to 7 days prior and 14 days post cycle 2) or pre surgery if this is not possible
- End of chemotherapy treatment (NOT end of mifamurtide treatment if applicable)
- At clinic visit during follow up no more than 6 monthly.
- At relapse (local recurrence or metastases)

10.5.2. ctDNA Processing and shipping

Whole blood should be collected into 2 x 10 mL BD Vacutainer® PAXgene ccfDNA blood collection tubes and inverted 10 times to mix. Samples must be shipped to RNOH on the day they are collected, using the shipping materials provided.

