11.4. Timelines for Data Entry

The relevant eCRFs must be completed as soon as possible after a patient's visit. Registration eCRFs must be completed for a patient to be registered onto the study. All other eCRFs must be completed within 7 days of the patient being seen.

Sites who persistently do not enter data within the required timelines may be suspended from recruiting further patients into the study by UCL CTC and this may trigger a monitoring visit. See section 14.2 ('Triggered' Onsite/Remote Monitoring) for details.

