APPENDIX 2: QUICK REFERENCE GUIDE TO PATIENT VISITS

Schedule: Patients Receiving Surgery Alone +/- Adjuvant Chemotherapy	Preregistration	Within 28 days after registration	Surgery	End of Treatment (After Adj Chemo, NOT mifamurtide)	Follow up	Relapse (local recurrence or metastases)	For registration For data collection For PROs For Tissue/Blood collection
Histological confirmation of osteosarcoma. Age & sex	Х						A. WHO PS for patients ≥16 years. Lansky PS for patients <16 years.
Informed consent	Х						B. Haematology: Hb, ANC, lymphocytes, platelets. Biochemistry: CRP, albumin,
Relevant Medical History		Х					ALP, LDH, Creatinine.
Cancer signs & symptoms		Х					C. If surgery is performed prior to registration.
Smoking status, Height and Weight		Х					D. In accordance with Osteosarcoma TMN version 8, 15/01/18.
WHO/Lansky PS ^A		Х	Х				E. For trial specific procedures only e.g. phlebotomy, relapse biopsy if not SOC.
Haematology & Biochemistry ^B		Х	Х	Х			F. SAM Booklet: Sarcoma Assessment Measure (SAM), EORTC QLQ-C30,
Data collected on primary tumour diagnostic imaging		Х					Toronto Extremity Salvage Score (TESS) and Global rating of change scale
Data collected on primary tumour biopsy/surgery ^c		Х					
Data collected on diagnostic imaging		Х					(GRCS) for patients 13 years and over only.
Osteosarcoma TNM staging ^D		Х					G. Annually from registration.
Data collected on treatment plan		Х					H. Complete within 3 months of registration (by parent/guardian if patient
Adverse Reactions (in relation to study procedures ONLY) ^E		X		X	Χ	X	<13).
SAM PRO Booklet (Patients ≥13 only) ^F		Х		Х	ΧG		I. To be taken at baseline, but can be taken later if this is not possible.
Diagnostic pathway questionnaires ^H		Х					J. Collect pre surgery.
Whole blood sample for germline DNA ^I		Х					K. Collected at clinic visit during follow up no more than 6 monthly.
Whole blood sample for ctDNA (optional for all patients)		ΧJ		Х	XK	X	L. Diagnostic Archival tissue - collection coordinated by UCL CTC.
Ship FFPE tumour tissue		Χ ^L	XM			Χ ^N	M. From routine surgery taking place after registration - collection coordinated
Collect frozen tumour tissue		Xo	Xo			Xo	by UCL CTC.
Collect information on frozen tumour tissue		Х	Х	Х		Х	N. If possible, collected from second sample at relapse if standard of care (SOC),
Disease status		Х	Х	Х	Χ		OR after Trial specific consent ONLY If not SOC.
Pre-operative imaging			Х				O. Relapse/Mets Frozen tissue sample will be SOC or optional for ICONIC

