Data collected on surgery			Х				research - collection coordinated by UCL CTC. Collect at indicated times but
Data collected on Adjuvant chemotherapy (if given)				Х			send on request
Data collected on radiotherapy including indication (if given)				Х			P. First and any subsequent relapses.
Survival status					Χ		Q. Continue to collect follow up eCRFs after the first relapse/metastasis form
Data collected on relapse (site, treatment etc.) ^P						Χ ^Q	has been completed

		days n	Duri	ing Tre	atment			nce		For registration
SCHEDULE: PATIENTS RECEIVING NEOADJUVANT CHEMOTHERAPY	Preregistration	Baseline: Within 28 da after registration	End of Neoadjuvant chemotherapy	Surgery	End of Adjuvant chemotherapy (NOT mifamurtide)	End of Treatment	Follow up	Relapse (local recurrence or metastases)		For data collection For PROs For Tissue/Blood collection
Histological confirmation of osteosarcoma. Age & sex	Х								A.	
Informed consent	Х								В.	, т,
Relevant Medical History		Х								LDH, Creatinine.
Cancer signs & symptoms		Х							C. D.	If surgery is performed prior to registration. In accordance with Osteosarcoma TMN version 8, 15/01/18.
Smoking status, Height and Weight		Х							E.	
WHO/Lansky PS ^A		Х		Х						SAM Booklet: Sarcoma Assessment Measure (SAM), EORTC QLQ-C30, Toronto
Haematology & Biochemistry ^B		Х		Х		Х				Extremity Salvage Score (TESS) and Global rating of change scale (GRCS) for
Data collected on primary tumour diagnostic imaging		Х								patients 13 years and over only.
Data collected on primary tumour biopsy/surgery ^C		Х							G.	1 7 1 10 11 11 11
Data collected on diagnostic imaging		Х							Н.	To be completed within 3 months of registration, by parent/guardian if patient
Osteosarcoma TNM staging ^D		Х								<13.
Data collected on treatment plan		Х							I.	To be taken at baseline, but can be taken later if this is not possible.
Adverse Reactions (in relation to study procedures ONLY) ^E		Х	Х		Х	Х	Х	Х	J.	For at least 50 neoadjuvant chemotherapy patients. If MAP chemo: collect 7-0 days prior to C2D21 methotrexate; If AP or other
SAM PRO booklet (Patients ≥13 only) ^F		Х				Х	ΧG		۲.	chemo: collect pre Cycle 3 (ideally up to 7 days prior/14 days post Cycle 2)
Diagnostic pathway questionnaires ^H		Х							L.	If not taken at end of neoadjuvant chemotherapy.
Blood sample for germline DNA ^I		Х							М.	Please take afterwards if not possible in 28 days after registration/before
Blood sample for CTCs ^J		Х	Χ ^K	Χ ^L				Х		treatment.

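### The total of mifamurtide cycles is requested at end of chemotherapy, a date the protocol separates from end of mifamurtide, and no later count is scheduled

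*Protocol*

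**What the plan says.** Section 9.4 sets the time point for three kinds of collection at once, clinical data, samples and PROs: "End of Treatment is defined as end of chemotherapy, and not end of treatment with Mifamurtide". Section 9.4.1 then lists what is due at that point. The list includes "Total number of mifamurtide cycles" and, on the next line, "If terminated early, provide reason".

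The separation of the two end dates is repeated elsewhere. Section 10.5.1 times a ctDNA sample at "End of chemotherapy treatment (NOT end of mifamurtide treatment if applicable"). In Appendix 2, the table for surgery with or without adjuvant chemotherapy heads its column "End of Treatment (After Adj Chemo, NOT mifamurtide"). The neoadjuvant table is laid out differently: the qualifier sits on "End of Adjuvant chemotherapy (NOT mifamurtide"), and End of Treatment is a separate column with no qualifier.

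On timing of entry, section 11.4 says "All other eCRFs must be completed within 7 days of the patient being seen". On purpose, section 2.3 includes among the unmet needs the study addresses "addressing variation in delivery of, and response to, standard therapies including chemotherapy and mifamurtide".

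**The concern.** A total can be known only once the drug has stopped. The protocol asks for it at a date that it takes care to distinguish from the end of that drug, so it allows for mifamurtide running on past the point of collection. For those patients the field holds a count to date, and nothing in the recorded value distinguishes it from a true total.

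The error is not spread evenly. It is zero for patients whose mifamurtide has already ended at end of chemotherapy, and it grows with the number of cycles given afterwards, so the longest-treated patients are under-counted most. At stake is the description of how mifamurtide is delivered across sites. Analyses of treatment patterns as a predictor of outcome under section 17.2.2.1 would also be affected if they draw on this field. An analysis plan cannot repair this, because it concerns what is collected and when.

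**Working it through.** The plan gives no figure to reproduce, and the documents contain no mifamurtide duration. The check is to trace every mifamurtide item and every later point at which treatment data could be recorded.

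1. **End of adjuvant chemotherapy (9.3.1).** Records whether mifamurtide was given and, if not, why. No cycle count and no stop date.
2. **End of Treatment (9.4 and 9.4.1).** The only place with a cycle count. Under 9.4 its date is end of chemotherapy. The line on early termination follows both the chemotherapy and the mifamurtide lines and does not say which it refers to. On either reading, it cannot cover a mifamurtide stop that has not yet happened.
3. **Follow-up (9.5.1).** Disease status, survival status, post-operative complications and adverse reactions to study procedures. No treatment item.
4. **Relapse (9.6.1).** Site of relapse and treatment received, listed as data due when relapse is confirmed. No first-line mifamurtide total.
5. **Appendix 2, both tables.** No mifamurtide data row, and no treatment row marked in the follow-up column.
6. **Corrections and deadlines (11.2, 11.4).** Sites may amend an eCRF that is not locked or frozen. Entry is due within 7 days of the patient being seen. Neither section tells sites to return to this field when mifamurtide ends.

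So item 2 is the sole quantitative mifamurtide field in the protocol, and nothing scheduled after it updates it.

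The consequence can be written without assumed numbers. Let *n* be the cycles given up to end of chemotherapy and *k* the cycles given afterwards.

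- Recorded total = *n*; true total = *n* + *k*; shortfall = *k*.
- Patient A continues and completes: recorded *n*, true *n* + *k*.
- Patient B has the same *n* and stops just after chemotherapy: recorded *n*, true *n*.

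A and B have the same record although one completed and the other did not. Neither *n* nor *k* is in the documents, nor is the number of patients with *k* above zero, so neither the shortfall per patient nor the effect on the cohort can be computed.

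The neoadjuvant table adds a second problem. A site working from section 9.4 enters *n*. A site working from that table could take the unlabelled End of Treatment column to mean the end of all treatment, wait, and enter *n* + *k*. The same field would then hold two different quantities, with no marker to tell them apart.

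**The case against.** Several points on the other side have force.

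- **Corrections are possible.** Section 11.2 allows changes to unlocked forms, and section 11.5 provides for central review and queries. The 7-day rule is a deadline for entry and does not forbid updating. A reader might infer that later cycles are lost for good. The documents do not support that: the eCRF and the database manual are not shown, and a site may update the field. What stands is narrower. The protocol schedules no later collection and gives no instruction to reopen the form.
- **Truncation need not be uniform.** A reader might infer that every patient still on mifamurtide gets a short count. The neoadjuvant table leaves room for some sites to enter the later figure. The explicit definition in 9.4 should govern, but the table means that practice may differ between sites. That is a further reason to reconcile the two.
- **No planned analysis names mifamurtide cycles.** Section 2.3 is background and speaks of concordance with a national algorithm. The Stage 2 objectives and section 17.2.2 do not mention mifamurtide completion or early stopping, and treatment patterns are not defined there as cycle exposure. Whether mifamurtide was given is captured. A reader might infer that a planned estimate is invalidated, but the protocol does not commit to one. The primary objective and the power calculations are untouched.
- **The size is unknown.** A percentage loss could be produced by assuming durations, but it would reflect only those assumptions.

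These points limit the consequence. They do not remove the conflict between the definition in 9.4 and the item in 9.4.1.

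**Conclusion.** The point holds as a conflict between a stated time point and a stated data item. Followed as written, sections 9.4 and 9.4.1 record a count to date under the name of a total for any patient who continues mifamurtide past chemotherapy. A later early stop and its reason have no scheduled place. The inconsistent column label in the neoadjuvant table may lead sites to fill the field differently.

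The effect is on the quality of mifamurtide delivery data, which section 2.3 presents as something the study addresses and which may enter treatment patterns in section 17.2.2.1. Its size cannot be quantified from the documents. The conclusion rests on the protocol's data lists, since the eCRF is not shown, and on the protocol's own premise that mifamurtide can end at a different time from chemotherapy. It does not rest on any assumed duration. It is worth correcting because the data item has a stated purpose and the correction is cheap.

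**What to change.** Keep End of Treatment at end of chemotherapy, and change the data items around it:

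- **Section 9.4.1:** replace the total with mifamurtide cycles to date and a status field (ongoing, completed or stopped).
- **Section 9.5.1 and the follow-up column of both Appendix 2 tables:** add the final number of mifamurtide cycles, the last-dose date and the reason if stopped early, collected at the first follow-up after mifamurtide ends. For patients already past that point, complete these from the medical notes.
- **Appendix 2, neoadjuvant table:** align the End of Treatment label with the definition in 9.4.

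The cost is a few extra eCRF fields, matching text in the sections named and some retrospective note review at sites. There are no new visits or procedures, and no treatment rule changes.

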9.4.2. End of Treatment: PROs

Patients aged 13 or over should complete the PROs (SAM, EORTC QLQ-C30, TESS, & GRC) at the end
of treatment.

